#### 5.2.5.2 Suicidality assessment

Suicidality assessment to further evaluate the psychological status of the subject will be performed at screening using the Columbia Suicidal Severity Rating scale C-SSRS. The C-SSRS is a brief measure which is designed to assess severity and change of suicidality by integrating both, behaviour and ideation. The C-SSRS was designed to address the need for a summary measure to track change in the severity of suicidality across both clinical settings and treatment trials.

The original Columbia Suicidal Severity Rating scale is shown in Appendix [10.2](#).

#### 5.2.5.3 Neurological examinations

As a general additional safety measure in the Dose Group 3, a physical neurological examination will be performed at the time points specified in the respective [Flow Chart](#).

The neurological examination will include the following assessments:

- General level of arousal
- Orientation
- Eye movement
- Pupil size and pupil reactivity
- Reflexes
- Assessment of muscle strength
- Gait
- Romberg test
- Tremor
- Point-to-point movements
- Sensitivity

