1. Subject must be informed and written informed consent obtained prior to starting any screening procedures. Screening procedures include physical examination, check of vital signs (including orthostatic testing), ECG, safety laboratory (including drug screening, hepatitis serology, HIV antibodies and syphilis), demographics (including determination of body height and weight, smoking status and alcohol history), relevant medical history, concomitant therapy and review of inclusion/exclusion criteria, Bowdle visual analogue scales and suicidality assessment (C-SSRS).
2. The time is approximate; the respective procedure is to be performed and completed within 2 h prior to drug administration. Allocation to treatment may be performed at any time following enrolment but must be completed prior to drug administration.
3. If several actions are indicated at the same time point, the intake of meals will be the last action.
4. End of trial examination includes physical examination, body weight, vital signs, ECG, safety laboratory, recording of AEs and concomitant therapies, Bowdle visual analogue scales and suicidality assessment (C-SSRS).
5. Only urine drug screening and alcohol breath test will be done at this time point.
6. AEs and concomitant therapies will be recorded throughout the trial, but will be specifically asked for at the time points indicated in the [Flow Chart](#) above.
7. Safety laboratory to be taken and to be medically evaluated on Day -1; this safety laboratory can be omitted, if the screening examination is performed on Days -3, -2 or -1.
8. The ECG recording has to be performed as triple at this time point
9. A blank urine sample (x) is to be obtained prior to administration of trial medication. Other urine samples are to be collected over the stated post-dose intervals (◀—|—|→) 0-4, 4-8, 8-12, 12-24, 24-48, 48-72 and 72-96 h.
10. One blood sample for pharmacogenomics analyses will be taken at any time after administration on Day 1.
11. Confirmation of fitness includes physical examination, vital signs, ECG, recording of AEs and concomitant therapies, Bowdle visual analogue scales and suicidality assessment (C-SSRS).
12. A blank urine sample for PK is to be obtained within 3 h prior to drug administration.
13. Safety laboratory samples will be collected after the subjects have fasted for at least 10 h except 4h on Day 1.

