	29	672:00	09:00	Ambulatory visit		x								x	x
3	29 to 33			End of trial (EOT) examination 	x				x	x	x	x		x	x

PK: pharmacokinetics, ECG: electrocardiogram, AE: adverse event

Proprietary confidential information © 2019 Boehringer Ingelheim International GmbH or one or more of its affiliated companies

1. Subject must be informed and written informed consent obtained prior to starting any screening procedures. Screening procedures include physical examination, neurological examination, check of vital signs (including orthostatic testing), ECG, safety laboratory (including drug screening, hepatitis serology, HIV antibodies, and syphilis), demographics (including determination of body height and weight, smoking status and alcohol history), relevant medical history, concomitant therapy and review of inclusion/exclusion criteria, Bowdle visual analogue scales and suicidality assessment (C-SSRS).
2. The time is approximate; the respective procedure is to be performed and completed within 2 h prior to drug administration. Allocation to treatment may be performed at any time following enrolment but must be completed prior to drug administration.
3. If several actions are indicated at the same time point, the intake of meals will be the last action.
4. End of trial examination includes physical examination, neurological examination, body weight, vital signs, ECG, safety laboratory, recording of AEs and concomitant therapies, Bowdle visual analogue scales and suicidality assessment (C-SSRS).
5. Only urine drug screening and alcohol breath test will be done at this time point.
6. AEs and concomitant therapies will be recorded throughout the trial, but will be specifically asked for at the time points indicated in the [Flow Chart](#) above.
7. Safety laboratory to be taken and to be medically evaluated on Day -1; this safety laboratory can be omitted, if the screening examination is performed on Days -3, -2 or -1.
8. The ECG recording has to be performed as triple at this time point
9. A blank urine sample (x) is to be obtained prior to administration of trial medication. Other urine samples are to be collected over the stated post-dose intervals (◀—|—|→) 0-4, 4-8, 8-12, 12-24, 24-48, 48-72 and 72-96 h.
10. One blood sample for pharmacogenomics analyses will be taken at any time after administration on Day 1.

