11. Confirmation of fitness includes physical examination, neurological examination, vital signs, ECG, recording of AEs concomitant therapies and Bowdle visual analogue scales and suicidality assessment (C-SSRS).
12. A blank urine sample for PK is to be obtained within 3 h prior to drug administration.
13. Safety laboratory samples will be collected after the subjects have fasted for at least 10 h except 4h on Day 1.

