#### Documentation, Assessment, and Reporting

Results will be documented in source data at the clinical trial site and assessed for clinical relevance by an investigator, deputy investigator or sub-investigator. Clinically relevant findings of the neurological examination will be reported as Adverse Events (during the trial) or as baseline conditions (at screening). Case narratives may be written if necessary.

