## **6. INVESTIGATIONAL PLAN**

### **6.1 VISIT SCHEDULE**

Exact times of measurements outside the permitted time windows will be documented. The acceptable time windows for screening and the end of trial examination are provided in the [Flow Chart](#).

Study measurements and assessments scheduled to occur ‘before’ trial medication administration on Day 1 are to be performed and completed within a 2 h-period prior to the trial drug administration except PK urine sample. A blank urine sample for PK will be collected within 3 h before drug administration.

The acceptable deviation from the scheduled time for vital signs, orthostatic testing and ECG will be  $\pm$  10 min and laboratory tests will be  $\pm$  30 min for the first 4 h after trial drug administration and  $\pm$  30 min thereafter.

If several activities are scheduled at the same time point in the Flow chart, ECG should be the first and meal the last activity. Furthermore, if several measurements including venipuncture are scheduled for the same time, venipuncture should be the last of the measurements due to its inconvenience to the subject and possible influence on physiological parameters except for the orthostatic testing.

The acceptable deviation from the scheduled time for standardized neurological tests (conducted in Dose Group 3) is  $\pm$  90 min on Day 7.

For planned individual plasma concentration sampling times and urine collection intervals, refer to the Flow Chart. While these nominal times should be adhered to as closely as possible, the actual sampling times will be recorded and used for the determination of pharmacokinetic parameters.

If a subject misses an appointment, it will be rescheduled if possible. The relevance of measurements outside the permitted time windows will be assessed no later than at the Report Planning Meeting.

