### 7.3.4 Safety analyses

Safety will be assessed as defined by the endpoints listed in Section [2.1.2](#) and 2.2.2 based on the treated set (TS). Safety analyses will be descriptive in nature and will be based on BI standards.

For all analyses the treatment actually administered (= treatment at onset) to the subject will be used (any deviations from the randomised treatment will be discussed in the minutes of the Report Planning Meeting).

Treatments will be compared in a descriptive way. The placebo group in the safety evaluation will consist of all subjects treated with placebo, regardless of the dose group in which they were treated. The test treatment groups will be compared to the placebo group in a descriptive way. Tabulations of frequencies/proportions will be used for the evaluation of categorical (qualitative) data, and tabulations of descriptive statistics will be used to analyse continuous (quantitative) data.

Measurements (such as ECGs, vital signs, or laboratory parameters) or AEs will be assigned to treatments (see Section [5.2](#)) based on the actual treatment at the planned time of the measurement or on the recorded time of AE onset (concept of treatment-emergent AEs).

Therefore, measurements planned or AEs recorded prior to intake of trial medication will be assigned to the screening period, those between trial medication intake until the trial termination date will be assigned to the treatment period. These assignments including the corresponding time intervals will be defined in detail in the trial statistical analysis plan (TSAP). Note that AEs occurring after the last per protocol contact but entered before database lock will be reported to Pharmacovigilance only and will not be captured in the trial database.

Additionally, further treatment intervals (called analysing treatments) may be defined in the TSAP in order to provide summary statistics for other than above periods, such as combined treatments, on-treatment totals, or periods without treatment effects (such as screening and post-study intervals).

Adverse events will be coded using the Medical Dictionary for Regulatory Activities (MedDRA). Frequency, severity and causal relationship of AEs will be tabulated by

Proprietary confidential information © 2019 Boehringer Ingelheim International GmbH or one or more of its affiliated companies

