For more details see the TSAP ADS plan.

According to ICH E3 ([7](#)), AEs classified as ‘other significant’ needs to be reported and will include those non-serious and non-significant adverse events with

- (i) ‘action taken = discontinuation’ or ‘action taken = reduced’, or
- (ii) marked haematological and other lab abnormalities or lead to significant concomitant therapy as identified by the investigator or Clinical Trial Leader at the RPM.

An overall summary of AEs (including AESIs) will be presented.

The frequency of subjects with AEs will be summarized by treatment, primary system organ class (SOC) and preferred term (PT). Separate tables will be provided for subjects with other significant AEs according to ICH E3 ([7](#)), for subjects with serious AEs, for subjects with drug-related AEs, for subjects with drug related serious adverse events and for subjects with AESIs.

The SOC and PTs will be sorted by frequency (within SOC). The MedDRA version number will be displayed as a footnote in the respective output.

In addition, frequencies of subjects with non-serious AEs that had an incidence of > 5% for at least one treatment will be summarised by treatment, primary SOC and PT.

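### A neurological examination scheduled only in Dose Group 3 gives 200 mg an extra route for detecting AEs that the lower doses and 4 of 6 pooled placebo subjects lack (minor; a cheap sensitivity display would show its effect)

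*Protocol*

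**What the plan says.** Protocol 5.2.5.3 introduces an 11-item examination for one group: "As a general additional safety measure in the Dose Group 3, a physical neurological examination will be performed". Protocol 6.1 repeats the restriction when it sets the time window for "standardized neurological tests (conducted in Dose Group 3").

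The flow-chart footnotes agree. At discharge (96 h) in Dose Groups 1 and 2: "Confirmation of fitness includes physical examination, vital signs, ECG, recording of AEs and concomitant therapies". At discharge (144 h) in Dose Group 3: "Confirmation of fitness includes physical examination, neurological examination, vital signs, ECG". For Dose Group 3 at Day 29 to 33: "End of trial examination includes physical examination, neurological examination, body weight, vital signs, ECG, safety laboratory". Dose Group 3 is also examined at screening. The flow chart for Dose Groups 1 and 2 has no neurological examination.

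On reporting, Protocol 5.2.5.3 states: "Clinically relevant findings of the neurological examination will be reported as Adverse Events (during the trial"). The primary endpoint (Protocol 2.1.2) is the number and percentage of subjects with drug-related AEs. Under Protocol 7.3.4 the placebo group "will consist of all subjects treated with placebo, regardless of the dose group in which they were treated", and each test treatment is compared with it descriptively. SAP 7.8.1 plans: "The frequency of subjects with AEs will be summarized by treatment, primary system organ class (SOC) and preferred term (PT"), with a separate table for drug-related AEs.

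The visible SAP never mentions the neurological examination. SAP 7.8.5 covers the physical examination, the Bowdle scales and the C-SSRS. The only change from the protocol declared in SAP 4 concerns alcohol history.

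**The concern.** The dose groups are treated in sequence, and the way AEs are looked for changes at the step from 100 to 200 mg. A higher rate of drug-related nervous-system AEs at 200 mg could reflect the drug, the closer search, or both. The planned tables cannot separate these.

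Pooling placebo does not cancel the difference, because two thirds of the pooled group were not examined. Investigators know the dose level (Protocol 3.2), and signs of a dose-response count as an argument for causality (Protocol 5.2.6.1.7), so findings sought only at the top dose may also be judged related more readily.

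Protocol 3.2 discusses observer bias and time effects and still expects unbiased treatment comparisons. It does not mention unequal ascertainment. The results are meant to help define doses for later studies (Protocol 1.3), so the dose-by-dose reading is the one that matters.

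**Working it through.** **Coverage.** Three groups of 6 active and 2 placebo give 3 × 8 = 24, the total in Protocol 7.7. Pooled placebo is 3 × 2 = 6. Subjects with post-dose neurological examinations:

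- 200 mg: 6 of 6
- 50 and 100 mg: 0 of 12
- pooled placebo: 2 of 6, leaving 4 unexamined
- whole trial: 8 of 24, leaving 16 unexamined

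The SAP's total over all BI-treated subjects has 6 of 18 examined, the same one third as pooled placebo. The imbalance therefore affects the dose-by-dose comparisons and not the overall active-versus-placebo total.

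**Size under no drug effect.** Two quantities are assumptions, because neither is in the documents. Let p be the rate of drug-related AEs found by the routes common to all groups. Let q be the chance that an examined subject without such an AE gains one found only by the neurological examination. Each examined subject then adds e = (1 − p)q, and the expected rates are:

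- 200 mg: p + e
- 50 or 100 mg: p
- pooled placebo: p + (2/6)e

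The spurious difference is e against 50/100 mg and (4/6)e against pooled placebo. With p = 0 these are q and (2/3)q. The chance of at least one such subject among the 6 on 200 mg is 1 − (1 − e)^6.

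| q | p | vs 50/100 mg (points) | vs pooled placebo (points) | at least 1 of 6 |
|---|---|---|---|---|
| 5% | 0% | 5.0 | 3.3 | 26.5% |
| 10% | 0% | 10.0 | 6.7 | 46.9% |
| 20% | 0% | 20.0 | 13.3 | 73.8% |
| 5% | 20% | 4.0 | 2.7 | 21.7% |
| 10% | 20% | 8.0 | 5.3 | 39.4% |
| 20% | 20% | 16.0 | 10.7 | 64.9% |

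One subject is 1/6 = 16.7 points of the observed 200 mg rate.

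**Would a common AE window remove it?** Suppose each of the two post-dose examinations independently yields such an AE with probability 2%, 5% or 10% (again assumed), and p = 0. Then q = 1 − (1 − r)² = 4.0%, 9.8% or 19.0%, and the difference from pooled placebo is 2.6, 6.5 or 12.7 points. A window ending at Day 10 to 14, the end of trial for Dose Groups 1 and 2, drops the Day 29 to 33 examination but keeps the one at 144 h (Day 7). Then q = r, and the difference is 1.3, 3.3 or 6.7 points. The artefact is roughly halved but not removed.

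**The case against.** A reader might infer that 50 mg, 100 mg and most placebo subjects could not yield neurological AEs at all. The documents do not support that. Every group has spontaneous reporting and repeated AE questioning (Protocol 5.2.6.2.1), general physical examinations at discharge and end of trial whose clinically relevant changes are AEs (Protocol 5.2.6.1.1), and the Bowdle scales. Tremor, gait change or altered arousal can be recorded at any dose.

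The effect may well be small. Subjects are healthy men aged 20 to 45 with relevant neurological disorders excluded. The screening examination turns pre-existing findings into baseline conditions. A finding counts only if judged both clinically relevant and drug-related, and a sign newly seen at Day 29 to 33 may be hard to attribute to a single dose. The upper end of the assumed range has no support in the documents. The two placebo subjects of Dose Group 3 are examined identically under blind. No hypothesis is tested (Protocol 7.2), so no error rate is distorted, and with six subjects per dose individual cases can be reviewed from the listings.

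All of this stands and limits severity. It does not remove the unequal detection. Case review can separate examination-only findings reliably only if the route of detection was recorded, and no visible text asks for that. One limit on the check itself: Protocol 2.2.2, which Protocol 7.3.4 cites for safety endpoints, is not in the public text.

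**Conclusion.** The point holds as a minor one. Examination coverage is 6 of 6 at 200 mg, 0 of 12 at 50/100 mg and 2 of 6 in pooled placebo. The resulting bias can only raise the 200 mg rate relative to the others. Its size cannot be derived from the documents. For an assumed q of 5% to 20% with no background rate and no drug effect it is 5 to 20 points against 50/100 mg and 3.3 to 13.3 points against pooled placebo, and less with any background rate. These are illustrations, not estimates.

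A reader might go further and conclude that the primary comparison should be read only from AEs other than those found by this examination. That does not follow. AE questioning and the examination share time points at 144 h and end of trial, and no order between them is stated. A sign found on examination first would be dropped at 200 mg, while the same sign elicited by questioning at 50 mg would count. In a safety trial that could hide a true signal at the highest dose.

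**What to change.** - **CRF:** flag each AE first detected at the scheduled neurological examination and not by spontaneous report, AE questioning or the general physical examination. At shared time points, record AE questioning before the examination so that the flag has one meaning.
- **SAP 7.8.1:** keep the all-AE table as the primary display. Beside it, add a sensitivity row of subjects with drug-related AEs excluding flagged events, for the comparison across doses and with pooled placebo.
- **SAP 7.8.1:** show flagged AEs for Dose Group 3 only, with 200 mg (n = 6) beside the 2 placebo subjects of that group. This comparison has equal ascertainment.

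The cost is one CRF item, one table row and one small display; no procedure or subject is added. The downside is that the site must record how each AE was detected. The SAP should state that the sensitivity row does not replace the all-AE result.

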#### Documentation, Assessment, and Reporting

Results will be documented in source data at the clinical trial site and assessed for clinical relevance by an investigator, deputy investigator or sub-investigator. Clinically relevant findings of the neurological examination will be reported as Adverse Events (during the trial) or as baseline conditions (at screening). Case narratives may be written if necessary.

## **5.2.6 Assessment of adverse events**

### **5.2.6.1 Definitions of adverse events**

#### **5.2.6.1.1 Adverse event**

An adverse event (AE) is defined as any untoward medical occurrence in a patient or clinical investigation subject administered a medicinal product and which does not necessarily have to have a causal relationship with this treatment.

An AE can therefore be any unfavourable and unintended sign (including an abnormal laboratory finding), symptom, or disease temporally associated with the use of a medicinal product, whether or not considered related to the medicinal product.

The following should also be recorded as an AE in the CRF and BI SAE form (if applicable):

- Worsening of the underlying disease or of other pre-existing conditions
- Changes in vital signs, ECG, physical examination, and laboratory test results, if they are judged clinically relevant by the investigator

If such abnormalities already pre-exist prior to trial inclusion, they will be considered as baseline conditions and should be collected in the eCRF only.

#### **5.2.6.1.2 Serious adverse event**

A serious adverse event (SAE) is defined as any AE which fulfils at least one of the following criteria:

- Results in death
- Is life-threatening, which refers to an event in which the subject was at risk of death at the time of the event; it does not refer to an event that hypothetically might have caused death if more severe,
- Requires inpatient hospitalisation
- Requires prolongation of existing hospitalisation
- Results in persistent or significant disability or incapacity
- Is a congenital anomaly/birth defect
- Is deemed serious for any other reason if it is an important medical event when based upon appropriate medical judgment which may jeopardise the subject and may require medical or surgical intervention to prevent one of the other outcomes listed in the above definitions. Examples of such events are intensive treatment in an emergency room or at home for allergic bronchospasm, blood dyscrasias or convulsions that do not result in hospitalisation or development of dependency or abuse

The following events will be handled as 'deemed serious for any other reason'. An AE which possibly leads to disability will be reported as an SAE.

Proprietary confidential information © 2019 Boehringer Ingelheim International GmbH or one or more of its affiliated companies

#### 5.2.6.1.3 AEs considered ‘Always Serious’

Cancers of new histology and exacerbations of existing cancer must be classified as a serious event regardless of the time since discontinuation of the trial medication and must be reported as described in [5.2.6.2](#), subsections ‘AE Collection’ and ‘AE reporting to sponsor and timelines’.

In accordance with the European Medicines Agency initiative on Important Medical Events, Boehringer Ingelheim has set up a list of further AEs, which, by their nature, can always be considered to be ‘serious’ even though they may not have met the criteria of an SAE as defined above.

The latest list of ‘Always Serious AEs’ can be found in the eDC (electronic Data Capture) system, an electronic data capture system which allows the entry of trial data at the trial site. These events should always be reported as SAEs as described above.

